2 SYNOPSIS

PRODUCT NAME/NUMBER	CetuGEX™
PROTOCOL NUMBER	GEXMab52201
EUDRACT NUMBER	2013-003695-13
IND NUMBER	118026
DEVELOPMENT PHASE	Phase II
PROTOCOL TITLE	Randomized, controlled, open-label, multicenter, phase II study to evaluate the efficacy and safety of CetuGEX™ plus chemotherapy in comparison to cetuximab plus chemotherapy for the treatment of patients with stage III/IV recurrent and/or metastatic squamous cell carcinoma of the head and neck. (The “RESGEX” Study)
INDICATION	First line systemic treatment for stage III/IV recurrent and/or metastatic squamous cell carcinoma of the head and neck (SCCHN)
SPONSOR	Glycotope GmbH [name]
COORDINATING INVESTIGATOR	
OBJECTIVES	
Primary:
 
To evaluate the efficacy of CetuGEX™ for the treatment of patients with stage III/IV recurrent and/or metastatic SCCHN as compared to cetuximab (both in combination with platinum-based chemotherapy) in terms of progression-free survival (PFS).
 
Secondary:
 
To evaluate further efficacy criteria, safety and quality of life (QoL) of patients with stage III/IV recurrent and/or metastatic SCCHN treated with CetuGEX™ as compared to cetuximab (both in combination with platinum-based chemotherapy).
 
To assess pharmacokinetic (PK) parameters and profiles of CetuGEX™.
 
To assess efficacy and safety based on genetic markers for immune response (Fc-gamma receptor [FcγR] allotypes) and biomarkers.

STUDY DESIGN	
Randomized, controlled, multicenter, phase II study with first line treatment (six cycles of 5-fluorouracil and cisplatin in combination with CetuGEX™ vs. combination with cetuximab) followed by single-agent maintenance therapy (CetuGEX™ or cetuximab respectively). Following the first cycle, substitution of cisplatin by carboplatin is allowed in case of toxicity. Randomization to CetuGEX™ vs. cetuximab will be performed using a 1:1 ratio.
 
Randomization will be stratified by:
 
 • FcγRIIIa status (FF or FV or VV) • Oral cavity and oropharynx vs. other locations • Locally recurrent vs. metastatic disease

	
 • Epidermal growth factor receptor (EGFR) treatment naïve vs. EGFR treatment as part of multimodal therapy.

DATA SAFETY MONITORING BOARD
	
As soon as at least 10 patients per treatment arm have completed the second cycle of combination therapy, patient safety data will be reviewed by an independent data safety monitoring board (DSMB). After this, regular 6-monthly meetings will be scheduled until all ongoing patients have been treated for at least 6 months. For important reasons additional meetings may be scheduled by sponsor, medical monitor, coordinating investigator or DSMB as long as patients are at risk.

PLANNED NUMBER OF PATIENTS
	
A total of approximately 240 randomized patients.


STUDY ENTRY CRITERIA
	
Inclusion criteria:
 
 1. Patients with histologically confirmed recurrent and/or metastatic SCCHN not eligible for local treatment. 2. Patients with measurable disease according to Response Evaluation Criteria in Solid Tumors (RECIST) 1.1. 3. Patients aged at least 18 years at screening. 4. Eastern Cooperative Oncology Group (ECOG) performance status of 0 or 1. 5. Minimum life expectancy of 3 months. 6. Tissue samples available for specific disease and therapy related biological assessments. 7. If female and of childbearing potential, is non-lactating and has negative pregnancy test results at screening and prior to randomization. 8. If female, is either not of childbearing potential (defined as postmenopausal for at least 1 year or surgically sterile [bilateral tubal ligation, bilateral oophorectomy, or hysterectomy]) or willing to use highly effective contraceptives during study participation until 6 months after last administration of any study medication, particularly cisplatin or carboplatin, with a failure rate < 1% according to the Note for Guidance on non-clinical safety studies for the conduct of human clinical trials and marketing authorization for pharmaceuticals (CPMP/ICH/286/95) of the European Medicines Agency (EMA). 
Male patients who have partners of childbearing potential have to confirm adequate use of highly effective contraceptives during study participation until 6 months after last administration of any study medication, particularly cisplatin or carboplatin, as well.
 
 9. Willing and able to comply with the protocol. 10. Willing and able to provide written informed consent. 
Exclusion criteria:
 
 1. Prior systemic chemotherapy, except if given as part of a multimodal treatment for locally advanced disease which was completed more than 6 months prior to randomization. 2. Cetuximab or other EGFR targeting agent treatment, except if given as part of a multimodal treatment for locally advanced disease which was completed more than 6 months prior to randomization. 3. Surgery (other than minor interventions like diagnostic biopsy or intravenous port implantation) or irradiation within 30 days before randomization.

	
 4. Concomitant anti-tumor therapy or concomitant immunotherapy, live vaccines including yellow fever vaccination (as per cisplatinum Summary of Product Characteristics [SmPC]). 5. Concomitant corticosteroid treatment unless specified within the protocol. 6. Clinical evidence of brain metastasis or leptomeningeal involvement. 7. Patients with nasopharyngeal tumors. 8. Concomitant malignant disease, except for adequately treated tumors with high likelihood of being cured (e.g., basal cell cancer of the skin, cervical cancer or breast cancer in situ). Patients with other previous malignancies but without evidence of disease for at least 5 years will be allowed to enter the study. 9. Patients with renal or hepatic impairment (serum creatinine and bilirubin > 1.5 fold above the upper limit of normal ranges, creatinine clearance < 60 ml/min, and transaminase > 5 fold above the upper limit of normal ranges) and patients with hematology parameters outside the normal ranges (hemoglobin < 9 g/dl, absolute neutrophil count < 1500/mm³ and platelet count < 10⁵/mm³) at screening as well as patients with impaired auditory function or platinum-related neuropathy. 10. Clinically active infections ≥ Grade 2 using National Cancer Institute (NCI) Common Terminology Criteria for Adverse Events (CTCAE) version 4 and/or requiring intravenous antibiotics. 11. Known active hepatitis B or C. 12. Known human immunodeficiency virus (HIV) infection. 13. Myocardial infarction within 6 months prior to screening. 14. Symptomatic congestive heart failure (New York Heart Association [NYHA] Grade 3 or 4), unstable angina pectoris within 6 months prior to screening, significant cardiac arrhythmia, history of stroke or transient ischemic attack within 1 year prior to screening. 15. History of keratitis requiring medical interventions within the last 5 years or interstitial lung disease. 16. Patients with any other disorder that, in the opinion of the investigator, might interfere with the conduct of the study. 17. Patients with an unstable condition (e.g., psychiatric disorder, a recent history of drug or alcohol abuse, interfering with study compliance, within 6 months prior to screening) or otherwise thought to be unreliable or incapable of complying with the requirements of the protocol. 18. Patients institutionalized by official means or court order. 19. Receipt of any other investigational medicinal product within the last 30 days before randomization or any previous CetuGEX™ administration. 20. Prior allergic reaction to a monoclonal antibody, grade 3 infusion related reaction (IRR) or any grade 4 reaction to a monoclonal antibody. 21. Known sensitivity to any component of the investigational medicinal product (IMP) and medication used in this study.

INVESTIGATIONAL PRODUCT
	
Active substance: CetuGEX™, a chimeric monoclonal immunoglobulin G (IgG) antibody binding to the EGFR which is glyco-optimized and fully human glycosylated with an enhanced antibody-dependent cell-mediated

	
cytotoxicity (ADCC) activity against tumor cells.
 
Dose, route, frequency: Solution for infusion, to be administered once weekly. The initial dose will be 990 mg; subsequent doses will be 720 mg once weekly. The initial dose will be given as split-dose over 2 days with a priming dose of 60 mg on Day 0 and the remaining dose of 930 mg on Day 1.

REFERENCE PRODUCT	
Active substance: cetuximab, a chimeric monoclonal IgG antibody binding to the EGFR.
 
Dose, route, frequency: Solution for infusion, to be administered once weekly. The initial dose will be 400 mg/m² body surface area (BSA), subsequent doses will be 250 mg/m² BSA each. The maximum infusion rate for the initial dose must not exceed 5 mg/min. The maximum infusion rate for subsequent doses must not exceed 10 mg/min.

NON-INVESTIGATIONAL PRODUCTS	
Active substance: 5-Fluorouracil (5-FU)
 
Dose, route, frequency: Solution for intravenous injection. Doses of 1000 mg/m² BSA per day will be administered every 3 weeks (1 cycle of cisplatin or carboplatin treatment) as continuous intravenous infusion on Days 1-4 of each cycle.
 
Active substance: Cisplatin
 
Dose, route, frequency: Solution for infusion. Doses of 100 mg/m² BSA will be administered every 3 weeks (1 cycle), on Day 1 of each cycle.
 
Active substance: Carboplatin
 
Carboplatin may substitute cisplatin following the first cycle of therapy in case of toxicity.
 
Dose, route, frequency: Solution for infusion, to be administered at an area under the curve (AUC) of 5 mg/mL/min (using the Calvert formula for calculation) as a 1-hour intravenous infusion every 3 weeks (1 cycle), on Day 1 of each cycle. As per SmPC, carboplatin may not be used in patients with bleeding tumors.
 
Cisplatin (which is allowed to be substituted by carboplatin following the first cycle in case of toxicity) in combination with 5-FU will be administered for a maximum of 6 cycles, starting approximately 1 hour after CetuGEX™/cetuximab infusion on Day 1 of each cycle.

TREATMENT REGIMENS	
Combination treatment phase:
 
Eligible patients will be randomized to receive as first line treatment either CetuGEX™ or cetuximab in combination with chemotherapy (5-FU and cisplatin) for the maximum duration of 6 cycles of combined treatment. In case of toxicity, chemotherapy can be dose reduced, discontinued or, if later than the first cycle, switched to carboplatin. If corticosteroids are required, e.g., as premedication to prevent infusion related reactions, dexamethasone is to be used (unless contraindicated). If chemotherapy is discontinued earlier for any other reason apart from progression, patients will start the maintenance phase at that time.
 
Single-agent maintenance phase:
 
After completion or discontinuation of combination chemotherapy for any other reason apart from progression, the treatment will be followed by maintenance therapy receiving single agent CetuGEX™ or cetuximab, respectively. Single-agent maintenance therapy will be continued until progression of disease.
 
Follow-up:

	
A Safety Visit must be performed 28 (+2) days after the last administration of the study drug for all randomized patients. In case of treatment discontinuation due to reasons other than disease progression, patients will stay on the regular study schedule until disease progression is documented and will then attend a Final Examination Visit. In case of regular treatment discontinuation due to disease progression, the Safety Visit is identical to the Final Examination Visit.
 
After the Final Examination, patients will be followed-up by quarterly phone calls until death or for a maximum duration of 24 months after randomization of the last patient for assessment of overall survival.

PLANNED STUDY SITES
	
Approximately 40 study sites in Europe and the USA.


CRITERIA FOR EVALUATION
	
Primary efficacy endpoint: Progression-free survival (PFS) as assessed by the investigator.
 
Secondary endpoints
 
Efficacy endpoints:
 
 • PFS as assessed by independent centralized reading • Objective response rate (ORR; i.e., complete response [CR] + partial response [PR]) at the end of combination treatment • Best overall response rates (including maintenance therapy treatment) • Clinical benefit rate (CBR; i.e., CR + PR + stable disease [SD]) • Duration of response • Overall survival (OS) • Time to treatment failure (TTF) • QoL scores as assessed by European Oncology Research Trials Committee (EORTC) quality of life questionnaires (QLQ) EORTC-QLQ-C30 and EORTC-QLQ-H&N35. 
In addition, PFS and all secondary efficacy endpoints listed above will be analyzed by FcγRIIIa-allotype subgroups (i.e., FF, FV, and VV), by p16 status, by EGFR status, and other potential parameters, unless the sample sizes in subgroups are too low.
 
Pharmacokinetic endpoints: Antibody trough levels and PK profiles of CetuGEX™ will be assessed throughout the study.
 
Safety endpoints:
 
 • Incidence of adverse events (AEs) and serious AEs, including incidence of target/class-specific side effects (skin reactions, diarrhea) • IRRs • Physical and laboratory assessments • Vital signs • Electrocardiogram (ECG) 
In addition, the incidence of AEs will be analyzed by FcγRIIIa-allotype subgroups (FF, FV, VV).
 
Exploratory endpoints:
 
 • Immunogenicity: incidence of anti-drug antibodies (ADAs) • Immunological parameters: cytokine levels and immune cell status.

STATISTICAL METHODS	
Analysis Populations
 
• Intention-to-treat (ITT) population – all randomized patients• Safety Population – all patients having received treatment at least once.• Per-protocol (PP) Population – all patients in the ITT population and who have received treatment at least once without major protocol deviations as defined in the statistical analysis plan and finally decided in a Data Review Meeting before data base lock.• Pharmacokinetic Population – all randomized patients including the subset of patients who had blood samples collected for PK non-compartmental profiling, who had at least one measureable CetuGEX™ antibody concentration. 
Efficacy Analyses
 
Primary endpoint of the trial is PFS defined as time from randomization until disease progression (as assessed by the investigator) or death of any cause. If the patient is alive and without progression at the last time of observation, the PFS time will be censored at the time of the last tumor assessment.
 
The primary efficacy analysis for PFS will be based on the ITT population. A log-rank test will be used to test the null hypothesis of equal treatment effects at an overall significance level of 0.05. The primary efficacy analysis will not be stratified by the factors used for stratification at randomization in order to preserve the estimated power considering the high number of strata. As a sensitivity analysis, a proportional hazards regression model will be applied and the effects of the stratification factors, the p16 status, and the EGFR status will be estimated.
 
The Kaplan-Meier method will be used to estimate the survival functions. Median survival times together with their 95%-confidence intervals will be retrieved from the survival functions.
 
The analysis will be repeated for the PP population as a sensitivity analysis.
 
A Chi-squared test will be performed to evaluate the effects of treatment on response rates according to RECIST. A logistic regression model will be fit to estimate odds ratios for the association of stratification factors, the p16 status, and the EGFR status with response categories. 95%-confidence intervals will be calculated for the treatment differences in response rates.
 
Overall survival and TTF will be analyzed analogously to PFS on an ITT basis.
 
If subgroup sample sizes allow, analyses of the primary and secondary efficacy endpoints will be repeated for the FcγRIIIa-allotype subgroups (i.e., FF, FV, and VV), the p16 status subgroups as well as the EGFR status subgroups s, omitting the FcγRIIIa factor, the p16 status and the EGFR status factor, respectively.
 
Pharmacokinetic Analyses
 
A population PK analysis will be performed with samples from all patients. In addition, non-compartmental analyses to evaluate the PK profile will be performed for a subgroup of approximately 30 patients.
 
Safety Analyses
 
All AEs will be coded using Medical Dictionary for Regulatory Activities (MedDRA) and analyzed on Preferred Term (PT) and System Organ Class (SOC) level.
 
Treatment emergent adverse events (TEAEs) are defined as any AE which started or deteriorated at or after start of treatment. Incidences for TEAE will be calculated on PT level, on SOC level and globally by treatment group. On

---------------------	---

	
each analysis level, a patient will be counted only once. Frequencies for TEAE will also be given for causality and severity graded according to Common Toxicity Criteria (NCI-CTC; AE criteria Version 4.0). In addition, toxicity as evaluated via incidence of AEs will be analyzed by Fc-gamma receptor allotype subgroups (FF, FV, VV) The incidences of ADA will be summarized in frequency tables per treatment arm.
 
For biomarkers as well as hematology and biochemistry laboratory variables, descriptive summaries of observed values and changes from baseline will be presented by treatment arm. The assessments of laboratory variables concerning reference ranges and clinical relevance will be tabulated by visit for each clinical laboratory parameter by treatment arm (frequency tables). Additionally, for each laboratory parameter, shifts in assessments from baseline to the last on-study value will be presented by treatment arm (shift tables).
 
Descriptive summaries of observed values and changes from baseline will be calculated for vital signs. These summaries will be presented by visit and treatment arm.
 
Descriptive summaries of observed values and changes from baseline will be calculated for ECG variables. QT will be corrected according to Bazett. Frequency and shift tables will be presented for the classified values of QT_c as given by the International Conference on Harmonisation (ICH)-E14, as well as for the overall clinical assessment.
 
Finding in post-baseline physical examinations will be documented as AE and analyzed as part of the general AE analysis.


SAMPLE SIZE DETERMINATION
	
The log-rank test will be used to test the hypothesis that patients assigned to the CetuGEX™ arm have increased PFS compared to patients assigned to the control arm. The sample size calculation is based on the following assumptions:
 
 • The median PFS in the control arm is expected to be 5.6 months post randomization. • It is expected that the median PFS in the CetuGEX™ arm can be increased to 8.4 months corresponding to a hazard rate of 0.67. • The anticipated recruitment time is 24 months, anticipated time until PFS events are reached is 12 months after randomization of the last patient, follow-up for OS for at least 24 months after randomization of the last patient. • Drop-outs are expected to occur at times following an exponential distribution and resulting in a drop-out rate of 10% at the cut-off for PFS analysis. • Patients will be randomized in a 1:1 ratio. • The overall two-sided significance level will be 0.05 and the power to be maintained 80%. 
Based on these assumptions, approximately 240 patients have to be randomized to observe the required overall number of 192 events.
 
Assuming a corresponding effect on OS (hazard ratio 0.67) and a median overall survival of 10.6 months in the control group the number of survival events to be observed after a 24 months follow-up for survival will be 183.

STUDY AND TREATMENT
	
The overall study duration is expected to be approximately 48 months, assuming 24 months for recruitment and follow-up of the patients for at least

DURATION	
24 months after randomization of the last patient).
 
The sequence and maximum duration of the study periods and treatment for each patient will be as follows:
 
1. Screening: to be performed within 28 days prior to first infusion to assess general eligibility for this study.2. Combination treatment phase: maximum of 6 treatment cycles of combination treatment.3. Single-agent maintenance treatment: until disease progression.4. Follow-up: at least 24 months after randomization of the last patient. 
The patients will be treated until disease progression.

----------	---

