7 STUDY DESIGN

7.1 Overall Study Design and Plan

7.1.1 Overview

This is a phase II, randomized, controlled, multicenter study with first line treatment (6 cycles of 5-FU and cisplatin in combination with CetuGEX™ vs. combination with cetuximab) followed by single-agent maintenance therapy (CetuGEX™ or cetuximab, respectively).

The randomization to CetuGEX™ vs. cetuximab will be performed using a 1:1 ratio and will be stratified by:

- FcγRIIIa status (FF or FV or VV)
- Oral cavity and oropharynx vs. other locations

- Locally recurrent vs. metastatic disease
- EGFR treatment naïve vs. EGFR treatment as part of multimodal therapy.

The study will include 3 separate study periods following screening:

Combination treatment phase:

Eligible patients will be randomized to receive as first line treatment either CetuGEX™ or cetuximab in combination with chemotherapy (5-FU and cisplatin) for the maximum duration of 6 cycles of combined treatment. In case of toxicity, chemotherapy can be dose reduced, discontinued or, if later than the first cycle, switched to carboplatin. If discontinued earlier for any other reason apart from progression, patients will start the maintenance phase at that time.

As soon as at least 10 patients per treatment arm have completed the second cycle of combination therapy, patient safety data will be reviewed by an independent data safety monitoring board (DSMB).

Single-agent maintenance phase:

After completion or discontinuation of combination chemotherapy for any other reason apart from progression, the treatment will be followed by maintenance therapy with CetuGEX™ alone or cetuximab alone, respectively. Single-agent maintenance therapy will be continued until progression of disease or limiting toxicity.

Follow-up:

A Safety Visit must be performed 28 (+2) days after the last administration of the study drug for all randomized patients. In case of treatment discontinuation due to reasons other than disease progression, patients will stay on the regular study schedule until disease progression is documented and will then attend a Final Examination Visit. In case of treatment discontinuation due to disease progression, the Safety Visit is identical to the Final Examination Visit.

After the Final Examination, patients will be followed-up by quarterly phone calls until death or for a maximum duration of 24 months after randomization of the last patient for assessment of overall survival.

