9.9.3 Cisplatin

Prior to each cisplatin infusion the following criteria should be fulfilled:

- Leucocytes $\geq 3.5 \times 10^9/L$ or neutrophils $\geq 1.5 \times 10^9/L$
- Platelets $\geq 100 \times 10^9/L$
- Creatinine $\leq 1.5 \text{ mg}/100\text{ml}$
- Urea $< 25\text{mg}/100\text{ml}$

If the above mentioned criteria are not fulfilled at the planned day of infusion, chemotherapy will be delayed until the criteria are fulfilled. If the chemotherapy is delayed, the IMP (CetuGEX™ or cetuximab) administration may not be withheld and needs to be continued with weekly infusions as scheduled. If chemotherapy is delayed for more than 3 weeks (i.e., more than 6 weeks between 2 consecutive Day 1 platinum-based chemotherapy infusions), the chemotherapy will be stopped and the patient will continue with the single-agent maintenance therapy.

The patient's subsequent chemotherapy doses will all be **reduced to 75 % of the initial dose** if any of the following toxicity occurs at any time during a chemotherapy cycle:

- Febrile neutropenia (ANC $< 1.0 \times 10^9/L$, fever $\geq 38.5^\circ\text{C}$)
- ANC $< 0.5 \times 10^9/L$
- Platelets $< 25 \times 10^9/L$
- Non-hematological toxicity grade 3 (NCI-CTC version 4.0): dose may be reduced at the discretion of the investigator

Once a chemotherapy dose modification has occurred, the dosage may not be re-escalated for this patient.

Patients with febrile neutropenia or a delay in therapy due to myelosuppression will be treated with G-CSF on subsequent cycles.

Switching from cisplatin to carboplatin has to be considered if the following toxicity occurs at any time during a chemotherapy cycle:

- Creatinine increase $>$ Grade 1 (NCI-CTC version 4.0)
- Ototoxicity $>$ Grade 2 (NCI-CTC version 4.0)
- Sensory neuropathy $>$ Grade 2 (NCI-CTC version 4.0)

If any of the above mentioned occurs again under carboplatin, chemotherapy has to be discontinued and the patient will enter the single-agent maintenance phase.

For more detailed information, please refer to the SmPCs for cisplatin (Appendix F) and carboplatin (Appendix H).

9.9.4 5-Fluorouracil

Prior to each 5-fluorouracil infusion the following criteria should be fulfilled:

- Leucocytes $\geq 3.5 \times 10^9/L$ or neutrophils $\geq 1.5 \times 10^9/L$
- Platelets $\geq 100 \times 10^9/L$

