12 DATA SAFETY MONITORING BOARD

XXXXXXXXXXXXXXXXXX will establish an independent DSMB, whose task is to review periodically the relevant safety data and provide advice on the continuation, modification

or termination of the study. The DSMB will be comprised of 3 members, 2 of them being oncologists and one of them statistician. A study specific charter will define in detail the composition, responsibilities and procedures of the DSMB.

As soon as at least 10 patients per treatment arm have completed the second cycle of first line treatment, a first meeting of DSMB will be scheduled to review the patient safety data. After this, regular 6-monthly meetings will be scheduled until all ongoing patients have been treated for at least 6 months. Starting at the second DSMB meeting, in addition to review of patient safety data a descriptive analysis on progression and survival will be included to monitor a potential detrimental effect of the IMP. For important reasons additional meetings may be scheduled by the coordinating investigator, sponsor, medical monitor or DSMB members as long as patients are at risk.

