13.4.5 Interim Analysis

No formal interim analysis will be performed. Descriptive summaries of PFS and OS events, including point estimates and 95% confidence intervals of the hazard ratios, will be provided to the DSMB at all meetings starting from the second meeting (approximately 9 months after start of enrollment) in order to monitor potential detrimental effects of the investigational compound.

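### The first scheduled DSMB review waits for 10 cycle-2 completers in each arm, so early toxicity that prevents or delays completion postpones it and every later scheduled meeting

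*Protocol*

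**What the plan says.** The rule appears in the protocol synopsis ("As soon as at least 10 patients per treatment arm have completed the second cycle of combination therapy, patient safety data will be reviewed"), in protocol 7.1.1 ("As soon as at least 10 patients per treatment arm have completed the second cycle of combination therapy") and in protocol 12, which words it slightly differently ("As soon as at least 10 patients per treatment arm have completed the second cycle of first line treatment") and continues: "a first meeting of DSMB will be scheduled to review the patient safety data". SAP 3.1 and 4.1 repeat it. None of these sections adds a calendar date, a number-treated trigger or an enrolment pause.

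Later meetings are counted from the first: "After this, regular 6-monthly meetings will be scheduled until all ongoing patients have been treated for at least 6 months". Protocol 13.4.5 has PFS and OS hazard ratios go to the DSMB "starting from the second meeting (approximately 9 months after start of enrollment"), in order to detect harm. A discretionary route also exists: "For important reasons additional meetings may be scheduled by sponsor, medical monitor, coordinating investigator or DSMB as long as patients are at risk".

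Four other provisions decide who reaches the end of cycle 2:
- Protocol 9.9.1: a grade 3 or 4 infusion or hypersensitivity reaction ends CetuGEX treatment permanently.
- Synopsis and 9.3: a patient who stops all chemotherapy for a reason other than progression moves to maintenance.
- 9.9.3 and 9.9.4: chemotherapy may be delayed by up to 3 weeks while the antibody continues weekly; beyond that, "the chemotherapy will be stopped and the patient will continue with the single-agent maintenance therapy".
- 8.4: withdrawn patients are not replaced.

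**The concern.** The trigger counts patients who tolerated two cycles, and the slower arm sets the date. Each patient lost before the end of cycle 2 must be made up by a newly exposed patient who then takes at least six more weeks to count. The review thus moves later when early tolerability is poor, which is the situation it is meant to detect.

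The early tolerability of this combination is not established in the documents. The phase 1 summary in protocol 5.2 mentions no chemotherapy partner, so no earlier exposure to the combination is shown. It reports infusion reactions of any grade in 70% of patients, mostly mild or moderate and almost all at the first infusion. Protocol 5.3 speaks of a few grade 3 reactions, whereas 9.9.1 says there were no severe ones. These two statements need to be reconciled, because a severe reaction at the first infusion removes a patient from the count.

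At stake are the date of the first scheduled independent look at both arms, the number of patients exposed by then, and the start of the PFS/OS harm monitoring.

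**Working it through.** **Inputs from the documents.** About 240 patients over 24 months, randomized 1:1 (protocol 13.2): 240/24 = 10 per month, or 5 per arm per month if accrual is even. Cycles last 3 weeks (9.3), so two undelayed cycles take 42 days: 42/30.4375 = 1.38 months. The permitted 3-week delay adds 21/30.4375 = 0.69 months.

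**Assumption.** Let q be the share of an arm that does not complete cycle 2. The documents give no value, so a range is shown. The few days between randomization and first dose are ignored.

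**The plan's own figure.** With even accrual, the first review falls at 10/[5(1 − q)] + 1.38 months. For q = 0 this is 2.0 + 1.38 = 3.4 months. Six months later is 9.4, which agrees with the stated second meeting at about 9 months.

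**Even accrual, the same q in both arms:**
- q = 0.3: 10/3.5 + 1.38 = 4.2 months
- q = 0.5: 10/2.5 + 1.38 = 5.4 months
- q = 0.5 with a 3-week delay: 5.38 + 0.69 = 6.1 months

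**Random accrual.** With Poisson accrual, the waiting time to enrol the 10th eventual completer in an arm is gamma distributed with shape 10 and rate 5(1 − q) per month. The review falls at the expected later of the two arms' times, plus 1.38 months. CetuGEX patients randomized by then are 5 × that time. Cetuximab q is set at 0.10 (assumed). The comparator is the 10th patient per arm plus 42 days, whether or not cycle 2 was completed. The direct calculation agrees with simulation (20,000 runs per scenario).

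| CetuGEX q (assumed) | First review, 10/month | On CetuGEX by then | First review, 5/month |
|---|---|---|---|
| 0.10 | 4.0 months | 20 | 6.6 months |
| 0.30 | 4.4 months | 22 | 7.5 months |
| 0.50 | 5.4 months | 27 | 9.5 months |
| 0.70 | 8.0 months | 40 | 14.7 months |
| Trigger independent of completion | 3.7 months | 18-19 | 6.1 months |

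At planned accrual the shift against the completion-independent trigger is about 0.3, 0.7, 1.7 and 4.3 months. At q = 0.50, about 10 CetuGEX patients have already failed to complete cycle 2 by the time of the review.

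**Knock-on.** The second meeting, with the first hazard ratios, falls 6 months later: about month 11.4 at q = 0.50 (5.4 + 6), against 9.7 (3.7 + 6).

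**The case against.** The strongest reply is that oversight does not wait for this meeting. The trial is open label, SAEs in both arms are reported within 24 hours (protocol 11.2.6.1), severe infusion reactions are reported immediately (11.3.1), and the sponsor, medical monitor, coordinating investigator or DSMB may call a meeting at any time. Half of an arm stopping within six weeks would be noticed. This stands: a reader might infer that nobody would look at both arms until the trigger is met, and the documents do not support that. However, the ad hoc route is discretionary and has no threshold, and the SAE text does not route reports to the DSMB.

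A reader might also take every toxicity to delay the review. It does not. Dose reduction, a switch to carboplatin after cycle 1, or dropping one agent while continuing the others need not stop a patient from completing cycle 2. What counts as completed is not defined for the trigger; the strict full-cycle definition in SAP 7.2 is an exposure variable.

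The effect is small unless non-completion is high, and nothing in the documents supports rates of 50% or 70%. That is correct, and it limits the size of the point.

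The DSMB charter, which is not among the documents, might hold a backstop. That cannot be excluded, but the trigger is fixed in both the protocol and the SAP, and those texts should carry the remedy.

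**Conclusion.** The point holds for toxicity that prevents or delays completion of cycle 2: death, permanent withdrawal, stopping all chemotherapy, or chemotherapy delay. Under the rule as written, such toxicity can only move the first scheduled review, and the meetings timed from it, later. The shift is under one month up to 30% assumed CetuGEX non-completion, and about 1.7 and 4.3 months at 50% and 70%. Slower accrual enlarges it. The direction follows from the protocol's own rules; the size rests on assumed non-completion rates and on even or Poisson accrual at the planned rate.

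Three stronger readings are not supported:
- That the second meeting at about 9 months is unattainable even with full completion: 9.4 months (even accrual) to 9.7 (random accrual) fits an approximate figure.
- That the combination is known never to have been given before: the phase 1 summary is merely silent on chemotherapy.
- That events in non-completers escape review: the review covers patient safety data without restricting it to completers, so those events are seen late, not lost.

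This is a worthwhile and inexpensive improvement to a stated rule, not a failure of safety oversight.

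**What to change.** In the protocol synopsis, 7.1.1 and 12, in SAP 3.1 and 4.1, and in the DSMB charter, replace the trigger with: the first review takes place when at least 10 treated patients per arm have either completed cycle 2 or stopped combination therapy earlier for any reason, including death, or 6 weeks after the first dose of the 10th treated patient in each arm, whichever is earlier.

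The cost is one sentence, repeated in each place. No dose, visit, sample size or analysis changes. The drawback is slightly less completed-cycle data at the first review. With low toxicity the date hardly moves (about 0.3 months at 10% non-completion in both arms); with high early toxicity the review stays at about month 3.7 or earlier at planned accrual.
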